Protocol Title:	A Pilot Study of the Immunogenicity of a Two-dose Protoco for 9-valent Human Papilloma Virus Vaccination in Postpartum Girls and Women (15-45 years old) previously unvaccinated against HPV	
NCT No.:	04274153	
Sponsor:	Merck & Co., Inc.	
Principal Investigator:	[name] MPH Johns Hopkins University [name] Office: [contact] [contact]	
Date:	May 18, 2022	

Date: May 18, 2022 Principal Investigator: [name] Application Number: IRB00227941

JHM IRB - eForm A – Protocol

- Use the section headings to write the JHM IRB eForm A, inserting the appropriate material in each. If a section is not applicable, leave heading in and insert N/A.
- When submitting JHM IRB eForm A (new or revised), enter the date submitted to the field at the top of JHM IRB eForm A.

1. Abstract

The human papillomavirus (HPV) is the most common sexually transmitted infection (STI) in the United States (U.S.) and is responsible for a wide range of conditions, including cancers within the anogenital tract and the oropharynx. Each year in the U.S., HPV causes approximately 330,000 cases of precancerous cervical dysplasia and 12,000 cases of cervical cancer, the most common cancer in women attributable to HPV. In 2012, there were 249,512 prevalent cervical cancer cases and 4,092 deaths in the U.S. Although infection with HPV is extremely common and most women will become infected with HPV at some point in their lives, the majority of infections are asymptomatic. However, if infection persists, over time, precancerous disease can eventually develop into cancer and spread through the body. In October 2018, the FDA expanded the approved use of the HPV 9-valent vaccine to include mid-adult women and men 27-45 years of age. This vaccine prevents cervical cancer caused by 9 types of HPV, however the immunization rate in the US is poor. As most pregnant women receive some prenatal care, the postpartum period is ideal to educate and implement a HPV vaccination program. The vaccine requires three doses and some patients have a difficult time completing the series. Our objective of this pilot study is to determine whether a two-dose 9-valent HPV vaccination regimen is non-inferior to a three-dose regimen.

Research Hypothesis

A 2-dose HPV vaccination regimen will demonstrate a non-inferior immune response compared to historical controls who received a 3-dose regimen among 15-45 year old postpartum women.

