A commonly raised issue with vaccination of sexually active women is their likely prior exposure to HPV. Although vaccination is most effective before sexual exposure to HPV, vaccination of sexually active women remains highly effective and cost-effective. In an HPV vaccine efficacy trial with 18,644 women 15-25 years of age, including those who were sexually active, and average follow-up of 2.9 years, incidence of precancerous lesions of moderate grade 3 or worse (CIN2+) was 30% lower in the vaccinated arm.⁶ There also were 24.7% fewer cervical excision procedures to treat precancerous lesions in vaccine recipients. Higher uptake of HPV vaccine could not only reduce the number of women that require surveillance and procedures to treat precancerous cervical lesions, which are linked to anxiety,⁷ pain,⁸ and adverse obstetrical outcomes,⁹ but also reduce the associated medical costs estimated to be \$8 billion dollars.^{10,11} Natural infections produce low antibody titers but do not confer lifelong immunity.¹⁰ Subsequent HPV vaccination with the same HPV type will indeed produce a robust immune response,¹² however it does not eliminate any cervical disease that is present at the time of vaccination. Additionally, sexual exposure to HPV typically is limited to one type, therefore the 9-valent vaccine will contain other types in which the patient had not been exposed previously.¹³

Postpartum HPV Vaccine Studies

One of the main reasons the HPV vaccine has had such poor compliance is lack of access to care.¹⁴ Vulnerable women that would benefit most from the HPV vaccine are often otherwise healthy individuals with minimal interactions with the healthcare system. However, as most pregnant women receive some prenatal care, the postpartum period is ideal to educate and implement a HPV

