c. Justification and safety information if non-FDA approved drugs without an IND will be administered.

N/A

7. Study Statistics

- a. Primary outcome variable.
 - Anti-HPV16 antibody titers measured four weeks after the second dose.

b. Secondary outcome variables.

- Antibody titers to the other 8 HPV types
- Seropositivity for each HPV type after 1-dose and 2-doses
- Percentage of participants who complete 1-dose, 2-dose, or 3-dose vaccination
- Percentage of participants with baseline titers suggestive of natural infection or prior vaccination
- Characteristics and percentage of participants who completed study visits in-person using their own transportation, required Lyft, or requested a home-visit. Characteristics will include individual demographic characteristics, sexual reproductive health history, STI history, neighborhood median income based on zipcode and neigborhood deprivation index based on address.
- Thematic coding of field notes if home visits were conducted

c. Statistical plan including sample size justification and interim data analysis.

Geometric mean titer (GMT) ratios for each HPV genotype will be compared between the 2dose and 3-dose regimen. As a non-inferiority trial, the primary analysis will use the perprotocol analysis. One-sided 90% confidence intervals (adjusted for multiple comparisons) will be constructed for the primary immunogenicity, which is the accepted method of reporting noninferiority results. Antibody GMTs at month-7 (4 weeks after 2nd dose) among participants who received the 2-dose regimen will be compared with historical controls who received the 3-dose regimen.²⁴ The criteria for declaring non-inferiority will be defined as the lower bounds of the multiplicity-adjusted 90% CI for the ratio of antibody GMT greater than 0.67. This noninferiority margin was selected based on bridging studies used for licensure.²⁵

Table 1: Statistical Intervals²⁶

Confidence	Sample	Actual Distance	Standard
Level	Size (N)	from Mean to Limit	Deviation (S)

0.900	107	0.125	1.000
0.900	107	0.150	1.200

Estimating the standard deviation of the GMT ratio to be 1.2 based on preliminary data, a sample size of 107 will produce a one-sided 90% confidence limit with a distance from the mean to the limit of 0.15. That is, if the GMT mean ratio is \geq 0.82, we will be 90% confident that the true ratio is not less than 0.67. To allow for almost 28% attrition, we will enroll 231 subjects.

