Secondary endpoints include % seropositive at baseline (before administration of 1st dose), % of participants who seroconverted. Descriptive statistics will be performed. Additionally, we will determine if hormone levels are associated with seropositivity and GMTs.

Given the success of our home visits as a method to increase retention, we would like to write a separate paper (brief report) to share our methodology with other researchers.

De-identified serum samples will be shipped to a Merck designated laboratory to perform the proprietary assay for HPV antibodies. No PHI will be shipped. Shipment will occur at study end in one batch. Hormone levels will be shipped to OHSU for analyses.

d. Early stopping rules.

Participants will be temporarily or permanently removed from the study regarding a severe AE related to the vaccination. Any participants with a positive pregnancy test after the baseline visit will be permanently removed from the study.

Participants may voluntarily withdraw from the study for any reason at any time. The PI may withdraw participants before their scheduled termination visit in order to protect their safety, and/or if participants are unable or unwilling to comply with study procedures. During the study, any abnormalities identified by history, physical examination, or laboratory tests will be reassessed until resolution, an explanation is found, or up until one month if changes are deemed permanent.

8. Risks

a. **Medical risks, listing all procedures, their major and minor risks and expected frequency.** Risks of the proposed study include the risk of pain, infection, dizziness, swelling, bruising, or bleeding from the needle stick that can occur with phlebotomy. Risks commonly associated with venipuncture include bleeding, occasional bruising at the site of venipuncture, hematoma, or infection. Rare complications (1/100) include lightheadedness or fainting. Other risks include infection, damage to the vein, blood clot or stroke, if a large amount of air enter the vein, but these are rare. Early pregnancies may not be detected even with a known last menstrual period and urine pregnancy test. The vaccine is not a live virus and does not cause birth defects. Administration of the vaccine may cause injection site pain, injection site swelling, redness of the skin, allergic reactions, and/or headaches. The vaccine also has a small risk of syncope.

b. Steps taken to minimize the risks.

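### The primary HPV16 GMT ratio against non-randomised historical controls takes no account of baseline HPV16 serostatus, so a serostatus imbalance could shift it in either direction

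*Combined protocol and SAP*

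**What the plan says.** The primary outcome (section 7a) is the anti-HPV16 titer four weeks after dose 2. In section 7c the GMTs "among participants who received the 2-dose regimen will be compared with historical controls who received the 3-dose regimen". The controls are referenced to a published trial, and section 12 says that the sponsor's laboratory will supply historical data. Non-inferiority requires the lower confidence limit of the GMT ratio to exceed 0.67. Section 7c adds that "the primary analysis will use the perprotocol analysis", without defining that set, and that "One-sided 90% confidence intervals (adjusted for multiple comparisons) will be constructed for the primary immunogenicity", without giving the method or number of comparisons.

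Baseline serostatus does appear in the plan. Blood is taken at Visit 1 before dose 1 (section 4a), and section 4i sets the HPV16 cut-off at ≥20 mMU/mL. Its stated uses are secondary. Section 7b lists "Percentage of participants with baseline titers suggestive of natural infection or prior vaccination", and the secondary-endpoint text of section 7c covers the percentage "seropositive at baseline (before administration of 1st dose), % of participants who seroconverted", with descriptive statistics. Nothing links it to the primary ratio, and nothing describes the controls' serostatus.

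The Background (section 3) explains why the question arises: "A commonly raised issue with vaccination of sexually active women is their likely prior exposure to HPV". Section 5 excludes women with a prior vaccine dose but not those with prior infection.

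**The concern.** Randomisation would balance baseline serostatus on average. A historical comparison does not. If women already seropositive for HPV16 reach a different titer after vaccination, and their share differs between participants and controls, that difference becomes part of the GMT ratio and is read as an effect of the regimen. It could help a truly inferior regimen pass the 0.67 margin, or make an equivalent regimen fail.

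The planned reporting of baseline seropositivity would show the participants' share. It would not show the controls' share, and it would not fix in advance which women enter the primary ratio.

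**Working it through.** **1. The plan's own figure.** Inputs from section 7c: SD 1.2, N = 107, one-sided 90% limit.

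Distance = t(0.90; 106) × 1.2/√107 = 1.2896 × 0.1160 = 0.1496, against 0.150 stated. At SD 1.0 it is 0.1247, against 0.125 stated. Both reproduce, as does 0.82 − 0.15 = 0.67.

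That subtraction is on the ratio scale, and section 7c does not state the scale of the SD. Below I take 1.2 as a natural-log SD, as is usual for titers. On that reading the observed ratio needed would be 0.67 × exp(0.1496) = 0.778 rather than 0.82.

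Enrolment of 231 with 28% attrition leaves 231 × 0.72 = 166 evaluable, whereas 107 evaluable would need only 107/0.72 = 149 enrolled. That mismatch is a separate matter, but it is why both 107 and 166 appear below.

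**2. How imbalance enters the ratio.** Let k be the post-vaccination GMT of seropositive women divided by that of seronegative women, assumed the same in both groups. Let p and q be the seropositive shares in participants and controls, and R the true ratio within each serostatus stratum. The group mean log titers contain p·ln k and q·ln k, so

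observed ratio = R × k^(p−q).

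The documents give none of k, p or q. For a 10-point imbalance:

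| k | p−q = +0.10 | p−q = −0.10 |
|---|---|---|
| 1.5 | ×1.04 | ×0.96 |
| 2 | ×1.07 | ×0.93 |
| 3 | ×1.12 | ×0.90 |

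If k = 1 or p = q the multiplier is 1. If k < 1 the directions reverse.

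**3. Effect on the decision.** Assumptions: control GMT treated as fixed, k = 2, N = 107. Then SE = 1.2/√107 = 0.1160, |b| = 0.10 × ln 2 = 0.0693 and |b|/SE = 0.5975. The critical value is z = 1.2816 unadjusted, or 2.2865 for an assumed Bonferroni over nine types (0.10/9).

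- False non-inferiority at R = 0.67 is 1 − Φ(z − b/SE). At +10 points this is 1 − Φ(0.684) = 0.247 unadjusted and 1 − Φ(1.689) = 0.046 with Bonferroni.
- Power at R = 1.0 is Φ([ln(1/0.67) + b]/SE − z), with ln(1/0.67) = 0.4005. With no imbalance this is Φ(2.171) = 0.985 unadjusted and Φ(1.166) = 0.878 with Bonferroni. At −10 points it is Φ(1.573) = 0.942 and Φ(0.568) = 0.715.
- At 166 evaluable, SE = 0.0931. Bonferroni power is Φ(2.013) = 0.978 with no imbalance and Φ(1.269) = 0.898 at −10 points.

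| k = 2 | No imbalance | 10-point imbalance |
|---|---|---|
| False non-inferiority, unadjusted, N = 107 | 10% | 25% (+10) |
| False non-inferiority, Bonferroni, N = 107 | 1% | 5% (+10) |
| Power, unadjusted, N = 107 | 98.5% | 94% (−10) |
| Power, Bonferroni, N = 107 | 88% | 72% (−10) |
| Power, Bonferroni, N = 166 | 98% | 90% (−10) |

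For k from 1.5 to 3 at N = 107, false non-inferiority at +10 points is 18% to 37% unadjusted, or 3% to 9% with Bonferroni. Power at −10 points is 97% to 89% unadjusted, or 79% to 59% with Bonferroni.

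**4. Precision of the remedies.** Assume 20% of participants are seropositive (not in the documents) and keep the control GMT fixed. The distances are unadjusted, for comparison with the planned 0.150.

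Stratified: distance = t × 1.2 × √[(1−w)²/n0 + w²/n1], where w is the weight on the seropositive stratum and n0, n1 are the seronegative and seropositive counts. Restricted: distance = t × 1.2/√n0.

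| Evaluable | n0 / n1 | Stratified, w = 0.2 | Stratified, w = 0.1 or 0.3 | Seronegative only |
|---|---|---|---|---|
| 166 | 133 / 33 | 0.120 | 0.123–0.124 | 0.134 |
| 107 | 86 / 21 | 0.150 | 0.154–0.155 | 0.167 |

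**The case against.** The strongest reply is that the rule may exist elsewhere. The cited control trial or the sponsor's data may be limited to women seronegative for the type, and the undefined per-protocol set may be meant to follow that. This stands as far as it goes: the documents cannot show an imbalance. It does not close the point, because restricted controls set against unrestricted participants would themselves be mismatched.

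A reader might infer that the ratio is biased towards non-inferiority, because the Background says: "Subsequent HPV vaccination with the same HPV type will indeed produce a robust immune response". The documents do not support that. The sentence does not compare seropositive with seronegative women, so it fixes neither the size of k nor whether it exceeds 1. The Background also says that exposure is typically to one type and that natural infection leaves low titers, so a large HPV16-seropositive share cannot be presumed.

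A reader might also infer that the error rate necessarily exceeds its nominal 10%. With k = 2 and a 10-point excess it does so unadjusted (25%), but not under nine-way Bonferroni (5%). That adjustment is itself an assumption, since section 7a names one primary variable.

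Finally, this is a pilot, and serostatus is one of several differences from the controls. Both are true. But the plan sets a formal margin and decision rule, and for participants this difference is measured at baseline.

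**Conclusion.** The omission is real and worth correcting. It shows a potential bias of unknown size and direction, and does not show that the result would be wrong. The decision figures are illustrations that rest on the log-scale SD, a fixed control GMT, a common k and an assumed imbalance. They are milder for power at 166 evaluable than at 107. Confidence is medium, because the controls' serostatus rule cannot be seen from the documents. The case for change is that the participants' data are already being collected and that the rule can be set before any antibody result exists.

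**What to change.** Before serum goes for the single end-of-study batch assay:

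- Ask the sponsor for the serostatus rule applied to the historical controls and for their HPV16 GMTs by baseline serostatus.
- Define the per-protocol set, stating how women who are HPV16-seropositive at Visit 1 are handled.
- Pre-specify the primary HPV16 comparison like with like, using the Visit 1 sample and the section 4i cut-off. If controls exist in both strata, use a serostatus-stratified GMT ratio weighted to the participants' seropositive share. If only seronegative controls exist, compare them with baseline-seronegative participants and say that the conclusion applies to seronegative women. The research hypothesis refers to "historical controls who received a 3-dose regimen among 15-45 year old postpartum women" and carries no such limit.
- Report the seropositive share in both groups where available, and give the unrestricted ratio as a sensitivity analysis.

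The cost is plan wording and a more specific data request, which section 12 does not guarantee will be met. No new samples are needed. On the assumed 20% share, stratifying costs almost no precision. Restriction still meets the planned distance with 133 women but misses it with 86; the latter means only 107 of 231 evaluable (1 − 107/231 = 54% attrition, against 28% planned). A small seropositive control group would add error that these figures leave out. A titer cut-off may miss some previously infected women. Other differences from the controls, such as postpartum status and dose-2 timing, would remain.

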In 2006, the Federal Drug Administration (FDA) approved a quadrivalent HPV vaccine that prevents infection against four common HPV types (i.e. 6, 11, 16, and 18) that are responsible for 70% of cervical cancer cases. The vaccine is administered as a series of three doses at 0-months, 1-2 months, and 6-months. Then in 2014, the FDA approved a 9-valent vaccine that prevented infection from five additional HPV types (31, 33, 45, 52, and 58) that are responsible for 20% of cervical cancers. Until recently, the multi-dose HPV vaccine regimen has been recommended for children 11-12 years old, with catch-up or permissive immunization through age 26. However, the immunization rate of the HPV vaccine in the US is disappointing: overall, only 49% of adolescents (ages 13-17) are fully immunized.⁵ In addition, although women who are poor or from racial or ethnic minority groups have disproportionately high rates of cervical cancer, their rates of HPV immunization are low. In October 2018, the FDA expanded the approved use of the HPV 9-valent vaccine to include mid-adult women and men 27-45 years of age. Given the low uptake in adolescents, sustained efforts for catch-up immunization are critical to address missed opportunities to protect adults against HPV-associated diseases.

Vaccination Post-Sexual Exposure

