Participants biologically born as females between the ages of 15 through 45 who are willing to have the HPV vaccine at the hospital after delivering a live born baby.

Exclusion Criteria

Severe allergic reaction to vaccine components, prior receipt of an HPV vaccine dose, fetal demise or stillbirth, allergy to yeast, moderate or severe acute illness (deemed by the investigator to exclude), and immunosuppression (e.g., HIV, solid organ transplant).

6. Drugs/ Substances/ Devices

a. The rationale for choosing the drug and dose or for choosing the device to be used. GARDASIL 9 is an inactive HPV vaccine that is administered intramuscularly and available in 0.5mL single does vials. GARDASIL 9 is commercially approved by the FDA for the prevention of cervical, vulvar, vaginal, and anal cancer caused by HPV types 16, 18, 31, 33, 45, 52, and 58. Participants will receive the recommended FDA dosage throughout the course of the study.

b. Justification and safety information if FDA approved drugs will be administered for non-FDA approved indications or if doses or routes of administration or participant populations are changed.

Gardasil-9 is FDA approved as a 3-dose series for patients 15-45 years old, and as a 2-dose series for patients 9-14 years old. In a 3-dose series, the second dose is usually given 1–2 months after the first dose, and the third dose is usually given 6 months after the first dose (0, 1–2, 6 month schedule). Per the Centers for Disease Control and Prevention, there are minimal intervals for administration of the HPV vaccine but no maximum intervals.²³ The minimum intervals are 4 weeks between the first and second dose, 12 weeks between the second and third doses, and 5 months between the first and third doses. If a vaccine dose is administered after a shorter interval, it should be re-administered after another minimum interval has elapsed since the most recent dose. If the vaccination schedule is interrupted, vaccine doses do not need to be repeated (no maximum interval). To stay in compliance, all participants will still receive 3 doses of the vaccine, although the scheduling is different. We are allowing enough time between doses (minimal interval) to allow an appropriate B-cell response and participants will complete the series within one-year. Therefore, this study aligns with the lack of a maximum interval and poses no change in risk compared to the traditional dosing schedule.

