There are not direct benefits to subjects who participant in this study, but the study has potential to provide key strategies to ensure completion of the HPV vaccine series among postpartum women.

10. Payment and Remuneration

Participants in the study will receive a total of \$75 dollars. \$25 will be dispensed at visit 2 and \$50 will be dispensed at visit 3. For participants who park in a Hopkins parking garage for visit 2 and visit 3, we will give them a patient/visitor parking coupon that will cover the cost of their parking for that visit. For participants arriving via bus, we will give them a bus token to cover the cost of their transportation. For participants unable to travel to visit 2 or 3 through the previous two methods, we will use a Lyft concierge service to call them a ride to and from the visit. The \$25 and \$50 compensation at visits 2 and 3, respectively, will be issued either through Venmo or a Visa gift card, depending on the participant's preference.

11. Costs

There is minimal no cost to the participant as vaccine costs are covered by grant funding.

12. Transfer of Materials

- a. Will you receive biospecimens from an external entity for this research? [No].
- b. Will you **transfer** biospecimens to an external entity as part of this research? [Yes] If "Yes", please address each of the following:

1) Describe the nature of the research collaboration with the external entity and the rationale for the transfer. (Include an explanation of your intellectual contribution to the design of the research study, resulting data and sharing, and participation in the planned publications.)

This study was designed by the PI and received support from Merck & Co.. Merck laboratory is responsible for testing antibody GMTs for each HPV genotype and providing historical data for us to compare. This ensure the feasibility of this clinical trials. Our results will be shared with Merck as the foundation for potiential larger clinical trials. People who made significant contibutions and are qualified for the authoship will be listed as one of the co-authors in the planned publications.

REFERENCES

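### The primary GMT ratio against historical 3-dose controls has no specified adjustment for age or baseline serostatus, and the resulting bias is of unknown size and direction

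*Combined protocol and SAP*

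**What the plan says.** The hypothesis in section 1 is that the 2-dose response is non-inferior "compared to historical controls who received a 3-dose regimen among 15-45 year old postpartum women". Section 5 admits "Participants biologically born as females between the ages of 15 through 45", with no age strata. It excludes earlier HPV vaccination but not baseline seropositivity.

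The primary outcome in section 7a is "Anti-HPV16 antibody titers measured four weeks after the second dose". Under section 7c, month-7 GMTs "among participants who received the 2-dose regimen will be compared with historical controls who received the 3-dose regimen", and non-inferiority is declared if the lower limit of the ratio exceeds 0.67. On adjustment, 7c says only this: "One-sided 90% confidence intervals (adjusted for multiple comparisons) will be constructed for the primary immunogenicity". It names a per-protocol analysis but does not define that set by age or serostatus. It specifies no covariate model, matching, weighting, age restriction or sensitivity analysis.

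The one planned demographic comparison (section 4a, Initial contact) is between participants and women who decline or are never approached. None is planned against the controls. Section 12 says the sponsor's laboratory is "providing historical data for us to compare", without stating the controls' ages or number, or whether the data are participant-level.

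**The concern.** Without randomisation, the GMT ratio estimates the regimen effect multiplied by the effect of every other difference between the cohorts. Two such differences can be measured and are left unhandled.

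- **Age.** The trial cohort may span 30 years of age, and nothing aligns the controls with it.
- **Baseline serostatus.** The Background (Vaccination Post-Sexual Exposure) says that vaccination after natural infection with the same type gives a strong response. A different share of seropositive women could therefore move the GMT. Section 7 treats baseline seropositivity only as a descriptive secondary endpoint.

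A shift upward could produce a false non-inferiority claim, and a shift downward could hide a true one. The interval in 7c covers sampling error only. The hypothesis also reads as though the controls were themselves postpartum women aged 15 to 45, which no part of the plan secures.

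**Working it through.** **Inputs from section 7c:** N = 107, SD 1.2, one-sided 90% limit, margin 0.67.

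**1. The plan's own figure.** Distance to the limit = t(0.90; 106) × SD / √N = 1.29 × 1.2 / √107 = 0.1496, which matches the stated 0.150. With SD 1.0 it is 0.1247, matching 0.125. The calculation is one-sample: it treats the control GMT as a known constant and uses no multiplicity adjustment.

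**2. Scale.** The plan does not say whether SD 1.2 is on the log scale, and it works additively (0.82 − 0.15 = 0.67). I read it as a natural-log SD. Then SE = 1.2/√107 = 0.116, and the log margin is ln(0.67) = −0.400.

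**3. Bias from age mix.** Let r be the older/younger GMT ratio and p the difference between cohorts in the share of older women. Both are assumptions. The ratio shifts by a factor r^p, and the share of the margin used is p·ln(r)/ln(0.67). If the shift favours two doses, the false-positive rate at a true ratio of 0.67 is Φ(|p·ln r|/0.116 − 1.29). If it runs against two doses, the chance of success at a true ratio of 1 is Φ((0.400 − |p·ln r|)/0.116 − 1.29).

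| r | p | Ratio shift | Share of log margin | False-positive rate, shift favouring 2 doses | Success at true ratio 1, shift against |
|---|---|---|---|---|---|
| none | none | 1.000 | 0% | 10% | 98.5% |
| 0.9 | 0.25 | 0.974 | 7% | 14% | 97.4% |
| 0.9 | 0.50 | 0.949 | 13% | 20% | 95.6% |
| 0.8 | 0.25 | 0.946 | 14% | 21% | 95.4% |
| 0.8 | 0.50 | 0.894 | 28% | 37% | 88.5% |
| 0.7 | 0.25 | 0.915 | 22% | 30% | 91.8% |
| 0.7 | 0.50 | 0.837 | 45% | 60% | 73.4% |
| 0.6 | 0.25 | 0.880 | 32% | 43% | 85.6% |
| 0.6 | 0.50 | 0.775 | 64% | 82% | 48.4% |

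The shift column is for a bias against two doses; the reciprocal applies in the other direction.

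**4. A single reference case.** A 10% shift is ln(1.10) = 0.095, or 0.095/0.400 = 24% of the log margin. The false-positive rate is Φ(0.095/0.116 − 1.29) = Φ(−0.47) = 32%. A shift of that size needs r = (1/1.10)^4 = 0.68 at p = 0.25, or r = (1/1.10)^2 = 0.83 at p = 0.50.

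**5. Effect of multiplicity adjustment.** The plan names no method. If it were Bonferroni over nine types, the critical value would be about 2.3. The false-positive rate would then be Φ(−2.3), about 1%, without bias, and Φ(0.82 − 2.3), about 7%, with the 10% shift. The absolute rates are lower, but the bias still multiplies the nominal rate.

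**The case against.** The strongest reply is that nothing in the documents shows the bias to be large. No section gives an age effect on titer within 15 to 45 years or describes the controls' ages. The whole scale in the working is assumed, and at r = 0.9 the share of the margin is only 7% to 13%. That stands.

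A reader might infer from two statements that age matters greatly here. One is "Gardasil-9 is FDA approved as a 3-dose series for patients 15-45 years old, and as a 2-dose series for patients 9-14 years old". The other is the Background's remark that two-dose non-inferiority has been shown in adolescents. Both concern a boundary at or near the trial's youngest age and say nothing about a gradient above it.

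A reader might also infer that the controls contain no women over 26, because the cited control source dates from 2015 and "In October 2018, the FDA expanded the approved use of the HPV 9-valent vaccine to include mid-adult women and men 27-45 years of age". The dates justify asking, but they do not establish the age range of the data to be supplied.

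Nor does 7c prescribe an unadjusted analysis; it is silent. For a prespecified primary analysis, silence still leaves a direct GMT comparison as the only one described.

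It is also fair that this is a declared pilot with openly historical controls, that participant-level control data are not promised, and that restricting the primary estimate to overlapping ages would narrow the target population. These points limit the remedy but do not remove the gap, because the plan still sets a formal rule for declaring non-inferiority.

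**Conclusion.** The point holds as an omission: 7c declares non-inferiority from a direct ratio against external controls, without adjusting for age or baseline serostatus or even comparing them between cohorts. Size and direction cannot be determined from the documents. Under the assumed ranges, age mix alone uses about 7% to 64% of the log margin. It reaches 45% or more only at r of 0.7 or below with a 50-point imbalance, or an equivalent combination. A claim that age mix does move the ratio by a large share of the margin is not supported.

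The false-positive figure of about 32% for a 10% shift is conditional on a natural-log SD of 1.2, N = 107, a control GMT without sampling error and an unadjusted one-sided 90% limit. Multiplicity adjustment lowers it. The effect of a serostatus difference is not quantified, because the documents give no figure for it. This is a cheap improvement.

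**What to change.** In section 7c:

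- Name the control dataset before any serum is assayed. Sera ship in one batch at study end, so this can be done before titers are known.
- Request the controls' age and baseline type-specific serostatus from the sponsor, at participant level or by age stratum.
- Prespecify a regression of log titer on regimen, age and baseline serostatus. If only grouped data are supplied, use age-standardised GMTs and state which population they are standardised to. Report the result with the crude ratio.
- Tabulate age and baseline serostatus for both cohorts, and add an analysis restricted to overlapping ages as a sensitivity analysis.

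In section 1, reword the hypothesis so that it does not imply postpartum controls. State that postpartum status cannot be adjusted for if the controls are not postpartum, since it would then coincide with group.

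The cost is a data request, one extra model and possibly a wider interval. The trial already collects demographics and pre-dose serum, so no participants or procedures are added.
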